9.1.5. Adverse events of specific interest

9.1.5.1. Potential immune-mediated diseases

Potential immune-mediated diseases (pIMDs) are a subset of AEs that include autoimmune diseases and other inflammatory and/or neurologic disorders of interest which may or may not have an autoimmune aetiology. AEs that need to be recorded and reported as pIMDs include those listed in [Table 19](#).

However, the investigator will exercise his/her medical and scientific judgement in deciding whether other diseases have an autoimmune origin (i.e. pathophysiology involving systemic or organ-specific pathogenic autoantibodies) and should also be recorded as a pIMD.

Table 19 List of potential immune-mediated diseases

Neuroinflammatory disorders	Musculoskeletal disorders	Skin disorders

 • Cranial nerve neuropathy, including paralysis and paresis (e.g. Bell's palsy). • Optic neuritis. • Multiple sclerosis. • Transverse myelitis. • Guillain-Barré syndrome, including Miller Fisher syndrome and other variants. • Acute disseminated encephalomyelitis, including site specific variants e.g.: non-infectious encephalitis, encephalomyelitis, myelitis, myeloradiculoneuritis. • Myasthenia gravis, including Lambert-Eaton myasthenic syndrome. • Demyelinating peripheral neuropathies including: 
 - Chronic inflammatory demyelinating polyneuropathy, - Multifocal motor neuropathy - Polyneuropathies associated with monoclonal gammopathy. • Narcolepsy. 	
 • Systemic lupus erythematosus and associated conditions • Systemic scleroderma (Systemic sclerosis), including: 
 - Diffuse Scleroderma - CREST syndrome • Idiopathic inflammatory myopathies, including: 
 - Dermatomyositis - Polymyositis • Anti-synthetase syndrome. • Rheumatoid Arthritis and associated conditions including: 
 - Juvenile Idiopathic Arthritis - Still's disease. • Polymyalgia rheumatica. • Spondyloarthropathies, including: 
 - Ankylosing Spondylitis, - Reactive Arthritis (Reiter's Syndrome), - Undifferentiated Spondyloarthritis, - Psoriatic Arthritis, - Enteropathic arthritis. • Relapsing Polychondritis. • Mixed Connective Tissue disorder. • Gout. 	
 • Psoriasis. • Vitiligo. • Erythema nodosum. • Autoimmune bullous skin diseases (including pemphigus, pemphigoid and dermatitis herpetiformis). • Lichen planus. • Sweet's syndrome. • Localised Scleroderma (Morphea).

Vasculitis	Blood disorders	Others

 Large vessels vasculitis including: 
 Giant Cell Arteritis (Temporal Arteritis), Takayasu's Arteritis. Medium sized and/or small vessels vasculitis including: 
 Polyarteritis nodosa, Kawasaki's disease, Microscopic Polyangiitis, Wegener's Granulomatosis (granulomatosis with polyangiitis), Churg–Strauss syndrome (allergic granulomatous angiitis or eosinophilic granulomatosis with polyangiitis), Buerger's disease (thromboangiitis obliterans), Necrotizing vasculitis (cutaneous or systemic), anti-neutrophil cytoplasmic antibody (ANCA) positive vasculitis (type unspecified), Henoch-Schonlein purpura (IgA vasculitis), Behcet's syndrome, Leukocytoclastic vasculitis. 	
 Autoimmune hemolytic anemia. Autoimmune thrombocytopenia. Antiphospholipid syndrome. Pernicious anemia. Autoimmune aplastic anemia. Autoimmune neutropenia. Autoimmune pancytopenia. 	
 Autoimmune glomerulonephritis including: 
 IgA nephropathy, Glomerulonephritis rapidly progressive, Membranous glomerulonephritis, Membranoproliferative glomerulonephritis, Mesangioproliferative glomerulonephritis. Tubulointerstitial nephritis and uveitis syndrome. Ocular autoimmune diseases including: 
 Autoimmune uveitis Autoimmune retinitis. Autoimmune myocarditis. Sarcoidosis. Stevens-Johnson syndrome. Sjögren's syndrome. Alopecia areata. Idiopathic pulmonary fibrosis. Goodpasture syndrome. Raynaud's phenomenon.
Liver disorders	Gastrointestinal disorders	Endocrine disorders

 Autoimmune hepatitis. Primary biliary cirrhosis. Primary sclerosing cholangitis. Autoimmune cholangitis. 	
 Inflammatory Bowel disease, including: 
 Crohn's disease, Ulcerative colitis, Microscopic colitis, Ulcerative proctitis. Celiac disease. Autoimmune pancreatitis. 	
 Autoimmune thyroiditis (Hashimoto thyroiditis). Grave's or Basedow's disease. Diabetes mellitus type I. Addison's disease. Polyglandular autoimmune syndrome. Autoimmune hypophysitis.

When there is enough evidence to make any of the above diagnoses, the AE must be reported as a pIMD. Symptoms, signs or conditions which might (or might not) represent the above diagnoses, should be recorded and reported as AEs but not as pIMDs until the final or definitive diagnosis has been determined, and alternative diagnoses have been eliminated or shown to be less likely.

In order to facilitate the documentation of pIMDs in the eCRF, a pIMD standard questionnaire and a list of preferred terms (PTs) corresponding to the above diagnoses will be available to investigators at study start as presented in [APPENDIX C](#). The list of PTs was created using MedDRA version 20.1.

9.2. Events or outcomes not qualifying as adverse events or serious adverse events

9.2.1. AECOPD

AECOPD are common in subjects with COPD. Because they are typically associated with the disease under study, only AECOPD meeting the definition of an SAE and occurring in the time period defined in Section 9.3.1 will be reported to GSK Biologicals as described in Sections 9.4.1 and 9.4.3.

9.2.2. Pregnancy

Female subjects who are pregnant or lactating at the time of vaccination must not receive additional doses of study vaccines but may continue other study procedures.

While pregnancy itself is not considered an AE or SAE, any adverse pregnancy outcome or complication or elective termination of a pregnancy for medical reasons will be recorded and reported as an AE or a SAE.

Note: The pregnancy itself should always be recorded on an electronic pregnancy report.

The following should always be considered as SAE and will be reported as described in Sections 9.4.1 and 9.4.3:

- Spontaneous pregnancy loss, including:
 - spontaneous abortion, (spontaneous pregnancy loss before/at 22 weeks of gestation)
 - ectopic and molar pregnancy
 - stillbirth (intrauterine death of foetus after 22 weeks of gestation).
- Any early neonatal death (i.e. death of a live born infant occurring within the first 7 days of life).
- Any congenital anomaly or birth defect (as per [CDC MACDP] guidelines) identified in the offspring of a study subject (either during pregnancy, at birth or later) regardless of whether the foetus is delivered dead or alive. This includes anomalies identified by prenatal ultrasound, amniocentesis or examination of the products of conception after elective or spontaneous abortion.

Furthermore, any SAE occurring as a result of a post-study pregnancy AND considered by the investigator to be reasonably related to the study vaccines will be reported to GSK Biologicals as described in Section 9.4.3. While the investigator is not obligated to actively seek this information from former study participants, he/she may learn of a pregnancy through spontaneous reporting.

9.3. Detecting and recording adverse events, serious adverse events and pregnancies**9.3.1. Time period for detecting and recording adverse events, serious adverse events and pregnancies**

All AEs starting within 29 days following administration of each dose of study vaccines (Day 1 to Day 30) must be recorded into the appropriate section of the eCRF, irrespective of intensity or whether or not they are considered vaccination-related.

The time period for collecting and recording SAEs will begin at the first receipt of study vaccines and will end at last study visit for each subject. See Section [9.4](#) for instructions on reporting of SAEs.

All AEs/SAEs leading to withdrawal from the study will be collected and recorded from the time of the first receipt of study vaccines.

In addition to the above-mentioned reporting requirements and in order to fulfil international reporting obligations, SAEs that are related to study participation (i.e. protocol-mandated procedures, invasive tests, a change from existing therapy) or are related to a concurrent GSK medication/vaccine will be collected and recorded from the time the subject consents to participate in the study until she/he is discharged from the study.

The time period for collecting and recording pregnancies will begin at the first receipt of study vaccines and will end at last study visit. See section [9.4](#) for instructions on reporting of pregnancies.

The time period for collecting and recording of pIMDs will begin at the first receipt of study vaccines and will end at last study visit. See section [9.4](#) for instructions on reporting of pIMDs.

An overview of the protocol-required reporting periods for AEs, SAEs, and pregnancies is given in [Table 20](#).

Table 20 Reporting periods for collecting safety information

Event	Screening Visit*	Visit 1 Dose 1	6 d post Dose 1	29 d post Dose 1	Visit 3 Dose 2	6 d post Dose 2	29 d post Dose 2	6 months post Dose 2	Study Conclusion
Timepoint		Day 1	Day 7	Day 30	Day 61	Day 67	Day 90	Day 241	Day 451
Solicited local and general AEs									
Unsolicited AEs									
AEs/SAEs leading to withdrawal from the study									
SAEs									
SAEs related to study participation or concurrent GSK medication/vaccine									
Pregnancies									
pIMDs									
Intercurrent medical conditions									

* i.e. consent obtained.

The double-bordered lines indicate timings of vaccination.

AE = adverse event; SAE = Severe adverse event; GSK = GlaxoSmithKline; pIMD = potential immune mediated diseases.

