^b Procedures indicated by this footnote need to be repeated if the subject has any medical condition (e.g. fever) that prevents his/her participation in the study within 29 days of Screening Visit. In that case, a re-Screening Visit must be scheduled as soon as possible and no more than 7 days from Day 29 (Day 30 - Day 36) during which the procedures indicated by this footnote need to be repeated. Same as for the initial screening, the chest X-ray only has to be redone if no chest X-ray/ CT scan is available within the last 3 months. Data obtained during re-screening procedures should be entered in the eCRF.

^c Pregnancy tests will be performed on **all** females of childbearing potential **at screening and prior to vaccination (Visit 1 and Visit 3) [(including those female subjects of childbearing potential who did not have a pregnancy test at screening because an X-ray/ CT scan was available within the last 3 months)]**. In case a chest X-ray will be performed (i.e. in subjects who do not have an X-ray / CT scan) the pregnancy test should be carried out prior to the chest X-ray and if a subject has a positive **pregnancy** test the chest X-ray should not be performed and the subject will be deemed not eligible for the study. Please also refer to Section 10.2.2. (Amended 27 March 2019)

^d Only if no chest X-ray/ CT scan available within the last 3 months.

^e Only for subjects in the sub-cohort for CMI.

^f Only if, in the opinion of the investigator, it is safe for the subject. Sputum samples can be either spontaneous or induced, as per investigator judgement.

^g Refer to Section 7.5 for more details on study procedures for subjects meeting contraindications to subsequent vaccination before administration of vaccine Dose 2.

^h The following information will be collected with the electronic Diary Card: COPD morning and evening symptoms (including EXACT-PRO questionnaire), smoking exposure history, local and general solicited AEs and Healthcare utilisation.

ⁱ Please refer to Table 20 for recording periods of local and general solicited AEs, AEs/SAEs leading to study withdrawal, SAEs, pregnancies and pIMDs. Solicited AEs will be collected up to Day 7 post- vaccination. Solicited AEs ongoing at Day 7 will be followed up until resolution (for a maximum of 30 Days). Unsolicited AEs will be collected for 30 days after each vaccination and thereafter only AEs leading to Withdrawal.

^j Only for Screening failures.

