9.5. Follow-up of adverse events, serious adverse events, and pregnancies

9.5.1. Follow-up of adverse events and serious adverse events

9.5.1.1. Follow-up during the study

After the initial AE/SAE report, the investigator is required to proactively follow each subject and provide additional relevant information on the subject's condition to GSK Biologicals (within 24 hours for SAEs; refer to [Table 22](#)).

All AEs documented at a previous visit/contact and designated as not recovered/not resolved or recovering/resolving will be reviewed at subsequent visits/contacts until 30 days after the last vaccination.

All pIMDs (serious or non-serious) and SAEs documented at a previous visit/contact and designated as not recovered/not resolved or recovering/resolving will be reviewed at subsequent visits/contacts until the end of the study.

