10.2.2. Subject withdrawal from study vaccines

A ‘withdrawal’ from the study vaccines refers to any subject who does not receive the complete treatment, i.e. when no further planned dose is administered from the date of withdrawal. A subject withdrawn from the study vaccines may not necessarily be withdrawn from the study as further study procedures or follow-up may be performed (safety or immunogenicity *according to protocol procedure*. (Amended 27 March 2019)

Information relative to premature discontinuation of the study vaccines will be documented on the Vaccine Administration screen of the eCRF. The investigator will document whether the decision to discontinue further vaccination/treatment was made by the subject himself/herself or by the investigator, as well as which of the following possible reasons was responsible for withdrawal:

- Serious adverse event.
- Unsolicited non-serious adverse event.
- Solicited adverse event
- Not willing to be vaccinated
- Other (specify).

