11.10. Analysis of safety

The analysis will be performed on the TVC.

The percentage of subjects with at least one **local AE** (solicited and unsolicited), with at least one **general AE** (solicited and unsolicited) and with any AE during the 7-day (Day 1 – Day 7) or the 30-day (Day 1 – Day 30) follow-up period will be tabulated after each vaccination and overall with exact 95% confidence interval (CI). The same computations will be done for Grade 3 AEs, for related AEs and for Grade 3 related AEs.

The percentage of subjects/doses reporting each individual solicited local (any grade, Grade 3) and general (any grade, Grade 3, related, Grade 3 related) AE during the 7-day (Day 1 to Day 7) follow-up period will be tabulated for each group as follows:

- Overall, the percentage of subjects with the symptom and its exact 95% CI.
- Overall, the percentage of doses with the symptom and its exact 95% CI.

- Per study vaccine dose, the percentage of subjects with the symptom and its exact 95% CI.

The exact 95% CIs will be calculated assuming independence between doses. For fever, additional analyses will be performed by 0.5°C increments.

The verbatim reports of **unsolicited** symptoms will be reviewed by a physician and the signs and symptoms will be coded according to the MedDRA Dictionary for Adverse Reaction Terminology. Every verbatim term will be matched with the appropriate preferred term (PT). The percentage of subjects with unsolicited symptoms during the 30-day follow-up period after any study vaccine dose with its exact 95% CI will be tabulated by group and by MedDRA PT. Similar tabulation will be done for the percentage of doses, for Grade 3 unsolicited symptoms, for unsolicited symptoms that resulted in a medically attended visit, for Grade 3 and causally related unsolicited symptoms and for unsolicited symptoms causally related to vaccination.

The number of subjects who experienced any **pIMD** or any **SAE** from first vaccination up to 12 months post-Dose 2 will be reported.

The number of subjects who experienced any **AE leading to study withdrawal**, from first vaccination up to study conclusion, or any **SAE related to study participation of concurrent GSK medication/ vaccination**, during the entire study period, will be reported.

Pregnancy from first vaccination up to study end for each female subject and pregnancy outcomes will be described in detail.

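### A non-serious AE that starts after the 30-day Dose 1 window and stops Dose 2 needs no full AE record if the subject stays in the study, because the extended collection rule names study withdrawal only

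*Protocol*

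**What the plan says.** All references are to the protocol.

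- **General window, Section 9.3.1:** "All AEs starting within 29 days following administration of each dose of study vaccines (Day 1 to Day 30) must be recorded".
- **Extension for withdrawals, Section 9.3.1:** "All AEs/SAEs leading to withdrawal from the study will be collected and recorded from the time of the first receipt of study vaccines". The matching row of Table 20 is also limited to withdrawal from the study.
- **Extension for serious events, Section 9.3.1:** "The time period for collecting and recording SAEs will begin at the first receipt of study vaccines and will end at last study visit". pIMDs are collected over the same period.
- **Table 6, footnote i:** "Unsolicited AEs will be collected for 30 days after each vaccination and thereafter only AEs leading to Withdrawal". The last word is unqualified here, but the opening sentence of the same footnote speaks of study withdrawal, as does footnote 6 of Table 7.
- **Section 10.2.2:** withdrawal from study vaccine is defined separately from withdrawal from the study, and such a subject may stay in follow-up. "Information relative to premature discontinuation of the study vaccines will be documented on the Vaccine Administration screen of the eCRF". The reasons to be documented include a serious AE, a solicited AE and "Unsolicited non-serious adverse event", with no time limit.
- **Section 9.5.1.1:** unresolved AEs "will be reviewed at subsequent visits/contacts until 30 days after the last vaccination".
- **Section 11.10:** the reporting line beyond the 30-day tables is for any "AE leading to study withdrawal", alongside SAEs and pIMDs. Vaccine discontinuation is not mentioned.

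**The concern.** Section 10.2.2 lets a site give a non-serious AE as the reason for stopping vaccine at any time. Section 9.3.1 requires that AE to be recorded only if it began within 30 days of a dose or if it took the subject out of the study. The two rules leave room for a coded reason with no AE record behind it.

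This matters in two ways. Describing safety and reactogenicity is the first-listed secondary objective, and subjects who stop an adjuvanted vaccine because of an AE are of direct interest for it. Also, Section 11.5.3 restricts the mTVC to subjects with two documented doses and places the primary efficacy analysis there. Withholding Dose 2 because of an AE is thus a post-randomisation exclusion from the primary analysis set, and comparing such exclusions between arms calls for the event itself as well as a code.

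**Working it through.** No sample size, power or error-rate figure bears on this point. The check is a day count followed by a comparison of the collection rules.

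**1. The uncovered interval**

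- Dose 1 is on Day 1, and its AE window is Day 1 to Day 30 (Section 9.3.1).
- Table 8 allows 60 to 75 days from Visit 1 to Visit 3, so Dose 2 falls between Day 1 + 60 = Day 61 and Day 1 + 75 = Day 76.
- Optimal schedule: Day 31 to Day 60, which is 60 − 31 + 1 = 30 days.
- Latest allowed visit: Day 31 to Day 75, which is 75 − 31 + 1 = 45 days.
- After Dose 2 there is no further dose to stop, so the gap exists only between the doses.

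**2. Which events fall through**

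All four conditions must hold: the AE is non-serious and not a pIMD; it starts in those 30 to 45 days; it leads to Dose 2 being withheld; and the subject stays in the study. If any one fails, another rule requires a record.

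**3. Whether another record closes the gap**

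- *Vaccine Administration screen (Section 10.2.2).* It captures who decided and a reason category. Section 10.2.2 does not ask for term, intensity, causality or outcome; those belong to the AE assessment in Section 9.3.3.
- *Table 6, footnote i.* The unqualified last word could be stretched to cover vaccine withdrawal. The footnote's first sentence, Table 7 footnote 6, Section 9.3.1 and Table 20 all point to study withdrawal.
- *Record-AEs row of Table 6.* It spans the Epoch 002 contacts, but footnote i limits what is to be collected at them.
- *Intercurrent medical conditions (Section 7.7).* These are recorded to judge per-protocol eligibility. They are not AEs with a causality assessment and are not in the Section 11.10 tables.
- *Withdrawals tabulated by reason (Section 11.7).* For analysis, Section 10.2.1 defines a withdrawal as a subject who did not return for the concluding visit. A subject who stops vaccine but completes follow-up is not one.

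None of these supplies the missing AE record.

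**The case against.** Much of the opposing case stands.

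- **The event is not lost altogether.** A reader might infer that AEs which stop the vaccine are not collected at all. That is wrong: Section 10.2.2 requires a reason for every vaccine discontinuation, and that code can be tabulated by arm. AEs with onset on Day 1 to Day 30 are fully recorded even if they later stop Dose 2.
- **Dose 1 tolerability.** A reader might also infer that it is understated. The documents do not support this. Solicited AEs for 7 days, all unsolicited AEs for 30 days, and SAEs and pIMDs to the last visit are collected after Dose 1 whether or not Dose 2 follows.
- **Other routes catch many stopping events.** Of the contraindications in Section 7.5, pregnancy and pIMDs are collected to study end, invasive or malignant cancer is a named example of a serious event in Section 9.1.2, and exacerbations are recorded as efficacy events.
- **Follow-up.** Section 9.5.1.1 might be read as ending review of a one-dose subject's AEs at about Day 31, before the Dose 2 decision. That treats Dose 1 as the last vaccination in hindsight. A site still expecting to give Dose 2 would keep reviewing an unresolved AE.
- **Left to the SAP.** Table lists commonly are, so a missing table alone would be no finding. Collection periods are different: they are fixed in the protocol, and no SAP can recover terms and causality that sites were not asked to record.

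**Conclusion.** The point holds in a narrow form. The protocol recognises AE-driven withdrawal from vaccine but does not require a full AE record when the AE is non-serious, not a pIMD, and starts between the end of the Dose 1 window and Dose 2. The exposed period is 30 to 45 days. The effect is incomplete description, by arm, of why some subjects lost Dose 2 and left the mTVC.

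The number affected is probably small, since four conditions must coincide, and the protocol gives no Dose 2 discontinuation rate from which to derive it. It may be tempting to assume that 2% to 5% of about 300 subjects per arm miss Dose 2 for an AE, giving 0.02 × 300 = 6 to 0.05 × 300 = 15. Those figures rest wholly on the assumed rate and include AEs from Day 1 to Day 30 that are recorded, so they do not measure the gap. Nothing here shows bias in the primary analysis, which Section 11.8 also repeats on the TVC and the FAS. This is a low-cost improvement to a collection rule.

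**What to change.** 1. In Section 9.3.1, Table 20 and Table 6 footnote i, widen the category of AEs and SAEs leading to withdrawal so that it covers withdrawal from the study or from study vaccine, collected from first vaccination. This aligns the collection rule with Section 10.2.2 and removes the ambiguity in footnote i.
2. In Sections 9.5.1.1 and 9.5.1.2, extend follow-up to AEs that led to vaccine discontinuation. This also settles what the end of review means for a subject who receives one dose.
3. In Section 11.10, report AEs leading to vaccine discontinuation by group, beside those leading to study withdrawal.

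The cost is wording in six places (Section 9.3.1, Table 20, Table 6 footnote i, Sections 9.5.1.1 and 9.5.1.2, and Section 11.10), a few more AE records to complete and follow, and one more table or listing. The eCRF already has an AE section and a field for the discontinuation reason, and Table 6 already has AEs recorded at Visit 3.
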